## 1. Background

1 in 8 women in the United States will develop invasive breast cancer, and of these women, 35-40% will be treated with a mastectomy. Subsequent breast reconstruction has benefits for self-esteem and quality of life (Albornoz). In 2013, over 95,000 reconstructive breast procedures were performed, 75,000 of which were expander/implant based reconstruction (ASPS).

The majority of breast reconstruction procedures are done in a staged manner. Tissue expanders are placed at the time of mastectomy. These are then used to stretch the remaining skin to allow for eventual placement of an implant at the second stage of reconstruction. The simultaneous use of acellular human dermal matrix (ADM) as an internal sling to support the expander is frequently used because of aesthetic benefits, reduced capsular contracture, reduced amount of submuscular dissection and decreased time to complete the reconstruction (Breuning, Sbitany). With increased use of dermal matrices, increased complications have been documented, particularly infection and/or seroma, with rates up to 12-18% (Chun, Antony, Kim, Wiechman, Selber) and relative risks of 2.47-2.73 (Kim). Complications can necessitate further surgical procedures, hospitalization and removal of the tissue expander, or the need to abandon reconstructive efforts. Methods to reduce these complication rates would have substantial benefit for many breast cancer survivors.

Seroma formation is thought to be caused by an inflammatory response to the biological material acting as a (initially) non-vascularized foreign body. The presence of a seroma under the mastectomy skin flaps can lead to increased incidences of wound dehiscence, infection and/or asymmetry in the reconstructed breast appearance, both of which can lead to removal of the expander.

Authors have described modifications in technique designed to minimize seroma formation. These include placing an additional drain to drain the sub-ADM space as well as the sub-mastectomy skin flap space, leaving these drains in longer by lowering the threshold volume per 24 hour period, and applying postoperative soft compression dressings (Ganske).

Traditional management of an established postoperative seroma consists of percutaneous aspiration, seroma catheter placement and/or operative exploration, irrigation and drain replacement. Operative management is used for seromas refractory to aspiration or for suspected infected seromas. Imaged percutaneous drainage can also be used for aspiration and/or drain placement and cultures of the fluid can be obtained. Even with this technique, persistent fluid collections and infection can still necessitate expander removal (Tong). The presence of seroma fluid is linked to other complications such as infection and skin flap necrosis (Brzeziński). Thus, successful management of this complication may decrease other associated complications and the need to abandon the reconstructive efforts.

## Form B: Medical IRB Research Description

Methods to reduce and treat complications have focused on operative technique and not on the tissue expander itself. The AlloX2 tissue expander has been developed specifically to reduce and treat these complications. The traditional tissue expander has a single port to allow injection of saline through the skin directly into the expander for gradual stretching of the overlying skin. The AlloX2 expander has the same injection port plus a second port which is connected to a perforated drain placed on the lower edge of the expander (see attached diagram). The location of both ports are identified by a magnet placed over the breast skin. This second port gives percutaneous access to the peri-expander space, thus allowing removal of seroma fluid under the mastectomy skin flaps. Seroma aspiration using this access port in the expander is safer than percutaneous aspiration, as it will reduce the potential for accidental puncture of the expander during standard percutaneous drainage. The aspirated fluid can be cultured in the setting of infection allowing identification of bacteria and determination of antibiotic sensitivities. Additionally, instillation of culture specific antibiotic solutions directly into the peri-expander space can be accomplished through the second port. Thus, use of this second port in the expander can be both diagnostic as well as therapeutic.

The AlloX2 expander is FDA approved, but randomized prospective controlled studies have not been done comparing it to the standard single port expander for equivalency. The ability to decrease reconstructive failures related to seromas will benefit patients undergoing post-mastectomy reconstruction and potentially will reduce the costs involved in treating complications.

FDA Indications for Use: 510(k) Number K140383 (letter attached)

“AlloX2 Tissue Expanders are intended for temporary (less than six months) subcutaneous or submuscular implantation to develop surgical flaps and additional tissue coverage required in a wide variety of applications, particularly to aid in reconstructions following mastectomy, to aid in the treatment of underdeveloped breasts and to aid in treatment of soft tissue deformities.

Additionally, the AlloX2 Tissue Expanders contain a silicone drain component which allows access to and drainage of latent fluids from the periprosthetic space. This drain component does not replace short-term, immediate, intraoperatively placed drains.” (FDA)

### 2. Objectives

The goal of this study is to compare the AlloX2 expander with the traditional single port expander for equivalency. Complication rates that will be tracked include seroma, mastectomy skin flap necrosis, infection, wound dehiscence, need for explantation of the expander. Management of seromas will be compared between the two groups. We hypothesize that the AlloX2 expander will be as effective in achieving the final outcome of completion of the second stage of reconstruction with equal or improved complication rates.

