## Form B: Medical IRB Research Description

expander breast reconstruction. Due to the nature of the surgery, the study cannot be blinded. Patients will be followed until completion of expansion and exchange for the permanent implant which typically takes 2 to 3 months. Risks factors that have been previously identified to be associated with increased postoperative complications include smoking, obesity, breast size, diabetes, radiation therapy, and expander fill volume will be identified. The final outcome is completion of expansion and exchange to permanent implant.

Standard operative procedure and postoperative care will be done. Both groups will have the same to external drains placed which is standard operative procedure. Complications will be noted at each postoperative clinic visit and entered into a database. Complication rates will be compared between the two groups and associations with risk factors will be analyzed. There will be no cross-over into the other group in case of reconstructive failure. Treatment failures will be treated in the same fashion in the two groups.

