### 4. Study Population

The study patients will be recruited from the University of Kentucky Plastic Surgery clinic. They will consist of patients referred for breast reconstruction following mastectomy(ies), unilateral or bilateral, for breast cancer or for positive gene mutation. Only patients who are suitable candidates for and who agree to undergo tissue expander/implant reconstruction will be offered participation in the study.

The anticipated number of patients to be enrolled is 60, 30 randomized to each type of expander. The proposed study period for enrollment is January 2016 – December 2016.

Exclusion criteria include age less than 18, patients who refuse expander/implant reconstruction, patients who are not medical candidates for expander/implant reconstruction from a soft tissue standpoint, patients who are anticipated to need postoperative radiation therapy. Non-English speaking individuals or decisionally impaired individuals will not be enrolled.

The study will not involve fetuses, neonates, children, pregnant women, prisoners, or institutionalized individuals. Due to the nature of this study, only women will be enrolled as this is the population that undergoes mastectomy and breast reconstruction. Subjects will be chosen irrespective of ethnic background.

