### 7. Research Procedures

The study patients will be randomized into one of two groups, one using the AlloX2 two port tissue expander and the other using the existing single port expander (Allergan™). The surgical procedure will follow standard acceptable guidelines for tissue expander reconstruction (Alderman). Patients will receive IV prophylactic antibiotics and the surgical site is prepped with chloraprep. The expander is placed under the elevated pectoralis muscle and an acellular dermal matrix which is pre-sterilized (Alloderm™). The initial volume in the expander is recorded. Two standard suction drains are placed in the mastectomy defect and are removed when the output is <20cc/24 hours over two days.

Patients will be followed weekly in clinic to observe for complications and expand the expander. Filling of the expander is done weekly, or at an interval acceptable to the patient. When the desired volume is achieved, the patient will be scheduled for expander replacement with the permanent implant. This procedure is the final endpoint for the study.

If a seroma is suspected and there are no signs of infection, the expander is accessed through the second port of the AlloX2. If seroma fluid is aspirated, the fluid is cultured. If a seroma is suspected and there are signs of infection, the seroma cavity is drained with the second port and appropriate antibiotics can be ordered.

Medical records are reviewed to collect patient demographics, co-morbidities (hypertension, diabetes), adjuvant/neoadjuvant chemotherapy, body mass index, smoking status, operative time, and area of dermal matrix used. Postoperative complications include seroma, infection, skin flap necrosis. Univariate analyses of independent variables will be done, with the use of dermal matrix and development of infection as the dichotomous dependent variable.

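### The goal is equivalence and the hypothesis reads as non-inferiority, but the plan gives no margin, interval rule or criterion for either, with 30 patients per arm

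*Combined protocol and SAP*

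**What the plan says.** Section 2 sets the goal: "The goal of this study is to compare the AlloX2 expander with the traditional single port expander for equivalency". Section 1 describes the evidence gap in the same terms, noting that "randomized prospective controlled studies have not been done comparing it to the standard single port expander for equivalency". The hypothesis in Section 2 points in one direction: AlloX2 is expected to be "as effective in achieving the final outcome of completion of the second stage of reconstruction with equal or improved complication rates".

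The analysis content is short:
- Section 2: "Management of seromas will be compared between the two groups".
- Section 3: "Complication rates will be compared between the two groups and associations with risk factors will be analyzed".
- Section 7: "Univariate analyses of independent variables will be done, with the use of dermal matrix and development of infection as the dichotomous dependent variable". This is not stated as a comparison of the two expanders.

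Section 3 names the main endpoint: "The final outcome is completion of expansion and exchange to permanent implant". Section 4 gives the size: "The anticipated number of patients to be enrolled is 60, 30 randomized to each type of expander". No section states a margin, a confidence level, a test, a power or a reason for 60.

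**The concern.** Equivalence and non-inferiority are conclusions about how large a difference has been ruled out. Each needs a margin and a rule fixed in advance, usually that a confidence interval lies inside the margin. The plan has neither, for completion or for any complication. The goal and the hypothesis also imply different designs: equivalence is two-sided, while no worse or better is one-sided.

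Without a criterion, what counts as equivalent would be settled after the data are seen, in an open-label study. The easiest default would be to read a non-significant comparison as equivalence. The Background links infection and seroma to further surgery, hospital admission and loss of the expander, so a materially higher rate that goes unrecognised would matter to patients.

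**Working it through.** **The plan's own figure.** The 60 patients cannot be reproduced. The documents give no margin, alpha, power, expected completion rate or dropout.

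**Inputs.**
- From the documents: 30 per arm (Section 4), 1:1 allocation (Section 3), and infection and/or seroma rates of up to 12-18% with dermal matrix (Section 1).
- Assumed: one yes/no outcome per patient, no dropout, 12-18% as the control rate, Fisher's exact test at two-sided 5%, and 80% power for the margins.

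**1. Chance of missing a real increase.** With control rate p and AlloX2 rate kp, sum Bin(a; 30, kp) × Bin(b; 30, p) over all outcome pairs (a, b) whose Fisher p-value exceeds 0.05. Take k = 2 for a doubling and k = 3 for a tripling.

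**2. What identical results leave open.** Take 4/30 in each arm, so p = 0.1333. The Wilson 95% limits are [p + z²/2n ± z√(p(1−p)/n + z²/4n²)] / (1 + z²/n).
- Centre: (0.1333 + 0.0640)/1.1281 = 0.1750.
- Half-width: 1.96 × √(0.003852 + 0.001067)/1.1281 = 0.1219.
- Limits: 0.0531 and 0.2968.

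The Newcombe half-width for the difference is √[(0.1333 − 0.0531)² + (0.2968 − 0.1333)²] = 0.182, or ±18 points. An observed 8/30 (AlloX2) v 4/30 gives −7 to +33 points with Fisher p = 0.33.

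**3. Smallest margin with 80% power when the true rates are equal.** The approximation uses SE = √(2p(1−p)/30).
- At p = 0.12, SE = √0.00704 = 0.0839. Non-inferiority at one-sided 0.025: (1.960 + 0.842) × 0.0839 = 0.235. Equivalence with a 90% interval: (1.645 + 1.282) × 0.0839 = 0.246.
- At p = 0.18, SE = √0.00984 = 0.0992. The same formulas give 0.278 and 0.290.

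Exact enumeration with Newcombe intervals gives the margins in the table.

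| Control rate | 12% | 15% | 18% |
|---|---|---|---|
| Doubling non-significant | 87% | 81% | 74% |
| Tripling non-significant | 51% | 36% | 22% |
| Mean 95% half-width, equal rates (points) | 17.5 | 18.5 | 19.4 |
| Non-inferiority margin, one-sided 0.025 (points) | 24.8 | 26.6 | 27.6 |
| Non-inferiority margin, one-sided 0.05 (points) | 21.8 | 23.5 | 24.6 |
| Two-sided equivalence margin (points) | 25.5 | 27.4 | 29.1 |

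Every margin exceeds the control rate in its column. With truly equal arms, the chance of showing two-sided equivalence is below 0.1% at a 10-point margin, 2-9% at 15 points and 32-49% at 20 points.

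**4. Lower control rates (assumed).** At 5% and 10%, a doubling is non-significant 98% and 90% of the time. The equivalence margin is about 20 and 25 points, and the mean half-width about 14 and 17 points.

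**5. Completion.** The documents give no rate. At an illustrative 90%, 27/30 in both arms leaves ±17 points, and 24/30 (AlloX2) v 27/30 gives −29 to +9.

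**The case against.** **The plan never equates non-significance with equivalence.** This is right. A reader might infer that the plan prescribes that error, but no section says so. The harm is a risk created by silence.

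**The numerical base is thin.** This also stands. The 12-18% is an upper figure for infection and/or seroma, is not a design input, and does not say whether it counts patients or breasts. Fisher's test, zero dropout and 80% power are assumptions. These points limit the figures, but the missing criterion does not depend on them. Section 4 admits bilateral cases, but counting breasts would not rescue the claim. In the most favourable case (all bilateral, breasts independent, 60 v 60), the smallest two-sided margin is still 18-21 points and a doubling is non-significant 47-69% of the time.

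**This is a small single-center study of a device described as FDA approved.** True, but the documents do not call it a pilot, and they state equivalence as the goal. If it was meant as a pilot, rewording is the remedy.

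**A large harm would surely show.** A reader might take this as reassurance, but the numbers do not support it. A tripling is missed 22-51% of the time at these rates.

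**Moving to estimation replaces the investigators' question.** This is fair, so a route that keeps their question is given below.

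A reader might also conclude that 60 is the wrong number. The documents do not support that either: with no margin, there is no required sample size to compare it with.

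**Conclusion.** The point holds and should be fixed, because it concerns the study's stated goal. As written, the plan cannot support a conclusion of equivalence or non-inferiority: no criterion exists for either, and the goal and the hypothesis do not agree on which is meant. That finding rests on the text alone.

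Adding a margin would not be enough without facing its size. Under the stated assumptions, 30 per arm supports only margins of about 22-29 points, wider than the background complication rate. The review makes no claim that the expanders differ or that the investigators intend to misread a null result.

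**What to change.** Keep 60 patients and change the claim.

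- **Section 2, goal.** Replace the equivalence phrase with: *to estimate the difference in second-stage completion and complication rates*. Word the hypothesis as an expectation of similar or better rates, which this study will not by itself establish.
- **Section 3, add.** *Completion (reported first) and each complication are counted once per patient and reported as a risk difference, AlloX2 minus single port, with a 95% CI (e.g. Newcombe). Both limits are reported, and the conclusion states the worst difference the interval leaves open. A non-significant test will not be reported as equivalence or non-inferiority.*
- **Expected precision.** State about ±17.5 to ±19.5 points at assumed rates of 12-18%, and about ±14 at an illustrative 5%. Note that the documents give no completion rate.

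The cost is wording and a less favourable stated claim. No patients or data are added.

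**Alternative.** If the investigators keep an equivalence or non-inferiority question, they should say which, on which outcome, with a justified margin and interval rule. They should also acknowledge that 30 per arm supports only about 22-29 points at these rates. Narrower margins cost patients. At 12-18% in both arms with 80% power, non-inferiority at one-sided 0.025 needs about 46-58 per arm for 20 points, 80-103 for 15 and 170-232 for 10. Two-sided equivalence needs about 48-63, 83-112 and 184-254.

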### 3. Study Design

A prospective 1:1 randomized, single center, open label study will compare the traditional 1-port tissue expander with the AlloX2 2-port expander placed during immediate tissue

## Form B: Medical IRB Research Description

expander breast reconstruction. Due to the nature of the surgery, the study cannot be blinded. Patients will be followed until completion of expansion and exchange for the permanent implant which typically takes 2 to 3 months. Risks factors that have been previously identified to be associated with increased postoperative complications include smoking, obesity, breast size, diabetes, radiation therapy, and expander fill volume will be identified. The final outcome is completion of expansion and exchange to permanent implant.

Standard operative procedure and postoperative care will be done. Both groups will have the same to external drains placed which is standard operative procedure. Complications will be noted at each postoperative clinic visit and entered into a database. Complication rates will be compared between the two groups and associations with risk factors will be analyzed. There will be no cross-over into the other group in case of reconstructive failure. Treatment failures will be treated in the same fashion in the two groups.

### 4. Study Population

The study patients will be recruited from the University of Kentucky Plastic Surgery clinic. They will consist of patients referred for breast reconstruction following mastectomy(ies), unilateral or bilateral, for breast cancer or for positive gene mutation. Only patients who are suitable candidates for and who agree to undergo tissue expander/implant reconstruction will be offered participation in the study.

The anticipated number of patients to be enrolled is 60, 30 randomized to each type of expander. The proposed study period for enrollment is January 2016 – December 2016.

Exclusion criteria include age less than 18, patients who refuse expander/implant reconstruction, patients who are not medical candidates for expander/implant reconstruction from a soft tissue standpoint, patients who are anticipated to need postoperative radiation therapy. Non-English speaking individuals or decisionally impaired individuals will not be enrolled.

The study will not involve fetuses, neonates, children, pregnant women, prisoners, or institutionalized individuals. Due to the nature of this study, only women will be enrolled as this is the population that undergoes mastectomy and breast reconstruction. Subjects will be chosen irrespective of ethnic background.

### 5. Subject Recruitment Methods and Privacy

Patients will be recruited from the University of Kentucky Plastic Surgery Clinic. [name], will determine if a participant meets eligibility criteria and will approach the patients during regularly scheduled clinical appointments in order to assess if they are interested in learning more about the study.

Eligible patients will be those undergoing immediate breast reconstruction with tissue expanders following mastectomy. A patient's acceptance or declination to be a part of this study will not affect the type of reconstruction performed on the patient, or their care in any way.

## Form B: Medical IRB Research Description

No advertisements of any form will be used with this study.

### 6. Informed Consent Process

Patients will be asked to sign the consent form after the investigators fully explain the study and risks. This will be done prior to randomization into one of two groups. There is no waiting period between informing the prospective subject and obtaining consent. Voluntary consent may be obtained by the principal investigator (PI) ([name]), as well as collaborating investigators who are authorized to obtain informed consent. The consent will contain information in line with IRB guidelines as to a brief background for the study, reason for their inclusion, risks, potential benefits, insurance coverage for injury, confidentiality, rights of the participant to refuse or withdraw, and guarantee to continuity of care should they refuse to participate or withdraw from the study, access to information, and payment for participation.

Written informed consent from the participant will be placed in their medical record and documentation of the informed consent process will be placed in the participant's progress notes. A signed informed consent form will be obtained by the investigator. The participant will receive a copy of the informed consent form.

### 7. Research Procedures

The study patients will be randomized into one of two groups, one using the AlloX2 two port tissue expander and the other using the existing single port expander (Allergan™). The surgical procedure will follow standard acceptable guidelines for tissue expander reconstruction (Alderman). Patients will receive IV prophylactic antibiotics and the surgical site is prepped with chloraprep. The expander is placed under the elevated pectoralis muscle and an acellular dermal matrix which is pre-sterilized (Alloderm™). The initial volume in the expander is recorded. Two standard suction drains are placed in the mastectomy defect and are removed when the output is <20cc/24 hours over two days.

Patients will be followed weekly in clinic to observe for complications and expand the expander. Filling of the expander is done weekly, or at an interval acceptable to the patient. When the desired volume is achieved, the patient will be scheduled for expander replacement with the permanent implant. This procedure is the final endpoint for the study.

If a seroma is suspected and there are no signs of infection, the expander is accessed through the second port of the AlloX2. If seroma fluid is aspirated, the fluid is cultured. If a seroma is suspected and there are signs of infection, the seroma cavity is drained with the second port and appropriate antibiotics can be ordered.

Medical records are reviewed to collect patient demographics, co-morbidities (hypertension, diabetes), adjuvant/neoadjuvant chemotherapy, body mass index, smoking status, operative time, and area of dermal matrix used. Postoperative complications include seroma, infection, skin flap necrosis. Univariate analyses of independent variables will be done, with the use of dermal matrix and development of infection as the dichotomous dependent variable.

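### Section 7 names dermal matrix use as a dependent variable, and no analysis by randomised arm is specified for the hypothesised final outcome

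*Combined protocol and SAP*

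**What the plan says.** The goal in Section 2 (Objectives) is to "compare the AlloX2 expander with the traditional single port expander for equivalency". The hypothesis follows: "We hypothesize that the AlloX2 expander will be as effective in achieving the final outcome of completion of the second stage of reconstruction". Section 3 (Study Design) names the same event as the final outcome. Section 7 says of the exchange operation: "This procedure is the final endpoint for the study".

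Section 2 also lists what is followed: "Complication rates that will be tracked include seroma, mastectomy skin flap necrosis, infection, wound dehiscence, need for explantation of the expander". Section 3 says that complication rates will be compared by group and that their associations with risk factors will be examined. Section 2 adds a between-group comparison of how seromas are managed.

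On surgery, Section 7 describes one operation for all study patients: "The expander is placed under the elevated pectoralis muscle and an acellular dermal matrix which is pre-sterilized". The data to be taken from the medical record include "operative time, and area of dermal matrix used". Section 7 then closes with the only sentence in the document that names a dependent variable: "Univariate analyses of independent variables will be done, with the use of dermal matrix and development of infection as the dichotomous dependent variable".

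**The concern.** Two things are wrong with this as an analysis plan.

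First, the closing sentence of Section 7 makes use of dermal matrix a dependent variable. Matrix is something the surgeon places during the operation under study. It is not a consequence of which expander was allocated, and on the procedure text it does not differ between patients.

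Second, the document says what the final outcome is and what is expected of it, but not how it will be analysed by arm. No section gives an effect measure, test, interval or analysis set for completion. In a small open-label trial, the summary of the hypothesised outcome could then be chosen after the results are known.

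**Working it through.** The point is mainly textual. The only sample-size figure is 60 patients, 30 per arm (Section 4, Study Population). It cannot be reproduced, because the document gives no margin, error rate, power or expected completion rate. The check below therefore sets the sections side by side.

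**Step 1. Can matrix use be a dependent variable?**
- Section 7 describes one operation that includes matrix, with no optional or arm-specific wording. Done as described, matrix use is 30/30 + 30/30 = 60/60. A yes/no variable with a single value has no association to estimate.
- Universal use is an inference from the procedure text. Eligibility (Sections 4 and 5) does not require matrix, and Section 1 (Background) says of general practice only: "The simultaneous use of acellular human dermal matrix (ADM) as an internal sling to support the expander is frequently used".
- If the inference fails and some operations omit matrix, the variable varies but records a surgical choice. It still says nothing about the effect of the expander.
- If the sentence means infection in matrix-assisted reconstruction, infection is the sole outcome and matrix is not a dependent variable at all.

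On each reading, infection is the only usable dependent variable in the sentence.

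**Step 2. What is specified by randomised arm?**

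| Item | Comparison by arm | Method given |
|---|---|---|
| Completion of the second stage | Intended, through the goal and hypothesis (Section 2) | None |
| Five complications of Section 2 | Stated for complication rates (Section 3) | None |
| Seroma management | Stated (Section 2) | None |

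Completion carries the hypothesis, yet it has neither a method nor an explicit sentence saying that its rate will be compared by arm.

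**Step 3. Does explantation stand in for completion?** Only in part. Need for explantation is among the tracked complications, so the Section 3 comparison covers it, and it overlaps with failure to complete. But a patient who is lost, or not yet exchanged when follow-up ends, has not completed and need not have been explanted.

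**Step 4. Scale.** With 30 patients per arm, one patient changes an arm's completion rate by 1/30 = 3.3 percentage points. The large-sample half-width of a 95% CI for the difference in completion, with the same true rate p in both arms, is 1.96 × √(2p(1−p)/30). The document gives no completion rate, so the values of p are assumptions:

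| Assumed p | Half-width (percentage points) |
|---|---|
| 0.80 | 20 |
| 0.85 | 18 |
| 0.90 | 15 |
| 0.95 | 11 |

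This shows what the proposed estimate would look like. The finding in Steps 1 to 3 does not depend on it.

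**The case against.** The strongest reply is that the Section 7 sentence was never meant as the main analysis. It speaks of univariate analyses of independent variables, which fits the risk-factor work promised in Section 3. The between-arm comparison is announced elsewhere, so a risk-factor sentence is not at fault for leaving out completion. Nor does it list its independent variables, so expander type is not excluded from them. The word for the dependent variable is singular, which suggests a slip in drafting around one intended outcome, infection.

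Most of this stands. A reader might infer that the trial plans no between-arm comparison, or that the primary analysis is of matrix and infection. The documents support neither reading: Sections 2 and 3 state that the expanders, the complication rates and the seroma management are to be compared. It is also fair to say that the complications have no specified method either; they are ahead of completion only in having an explicit sentence.

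Two things remain. Matrix use is misplaced as a dependent variable even in a risk-factor analysis. And if the sentence is set aside as secondary, the document contains no analysis statement for completion at all.

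**Conclusion.** The point holds in a limited form and should be fixed. Section 7 names as a dependent variable a component of the operation. That component is constant (60/60) if surgery follows the procedure text, and it is not an outcome of the expander even if it varies. Separately, no analysis by randomised arm is specified for the hypothesised final outcome.

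The gap in the analysis of completion is certain on the text. The claim that matrix use does not vary rests on inference from the procedure description. A reader might take that description to mean that every patient must receive matrix; eligibility does not say so, and the conclusion does not need it. Infection is a legitimate dependent variable, and nothing here faults a risk-factor analysis of it.

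The absent equivalence margin, the counting rule for bilateral patients and the handling of patients lost to follow-up are separate issues and are not part of this finding.

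**What to change.** Delete use of dermal matrix as a dependent variable. Keep the area of matrix, already collected, as a descriptor or covariate. Replace the closing sentence of Section 7 with wording such as:

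> Completion (expansion finished and the expander exchanged for the permanent implant) will be compared by randomised expander type in all randomised patients, counted per patient, as a risk difference with 95% CI. Each complication listed in Section 2 will be compared in the same way. Univariate associations of the recorded risk factors with infection are exploratory.

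The cost is one paragraph of wording and commitment to one effect measure. Other measures would be defensible; what matters is fixing one in advance. No new data are needed: expander type, completion and matrix area are already to be recorded, and all five complications are to be tracked under Section 2. Section 7 lists only seroma, infection and skin flap necrosis, so wound dehiscence and explantation should be added there for consistency.

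Until a margin is set, this interval estimates the difference between the expanders but does not establish equivalency.
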